TITLE PAGE

**Role of Linagliptin in improving renal failure by improving
CD34+ stem cell number, function and gene expression in renal
function impaired type 2 diabetes patients**

[name], MRCP (UK), PhD, FACP, FACE

George Washington University Medical Faculty Associates

[name]

[name]

Phone - [contact]

Protocol Version/Date: Version 6.9 / June 2017

PROTOCOL SYNOPSIS

Protocol Title:	Role of Linagliptin in improving renal failure by improving CD34+ stem cell number, function and gene expression in renal function impaired type 2 diabetes patients
Site Numbers & Names:	GWU Medical Faculty Associates
Research Hypothesis:	Both type 2 diabetes and CKD are associated with poor stem cell number and function. Poor viability and function of EPCs in CKD and diabetes affects the repair and regeneration of the endothelium and renal tubules. We hypothesize that use of Linagliptin (along with Insulin, metformin, or both) may help reduce cardiovascular risk by improving EPC survival and function above and beyond adequate glucose metabolism control.
Study Schema: Drugs / Doses / Length of Treatment)	We propose a 2-arm randomized, parallel group, longitudinal study of 12-week intervention duration. The 12-week time interval has been previously shown adequate to observe changes in biochemistry, EPCs and, importantly, pulse wave velocity (PWV) changes. Patients will be randomized to 2 groups: Control, (n=20), Insulin/Metformin + Lifestyle + Placebo. Treatment, (n=20) Insulin/Metformin + Lifestyle + Linagliptin 5mg.

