
Study Objectives:
 
 • Primary: • Secondary: 	
The primary objective is to ascertain if addition of Linagliptin improves CD34+ cell function and gene expression in early type 2 diabetes patients with CKD stage 1-3, which will be correlated to improvement in 24hr urinary protein estimation and creatinine clearance (obtained via micro-albumin/creatinine ratio from a spot urine sample).
 
The secondary objective is to correlate the cellular outcome measures with other measures of endothelial function such as:
 
 1. Arterial stiffness measures with pulse wave analysis and pulse wave velocity measurements 2. Serum biochemistry looking at surrogates of endothelial health, endothelial inflammation, appetite controlling hormone levels and fasting glucose, insulin and lipid profile. 3. Resting Metabolic Rate measurement 
Study Outcome Measures
 
Primary:
 
To investigate the effect of Linagliptin on Endothelial function in patients inadequately controlled (HbA1C ≥ 6.5 % to ≤ 10%) while being treated with stable Insulin, Metformin, or both.
 
 • Cellular markers. We will study pre and post Linagliptin treatment changes in number, function and gene expression of patients' peripheral blood-derived CD34+ cells. • 24hr urinary protein estimation and creatinine clearance. 
Secondary:
 
 • To investigate the effect of Linagliptin treatment on serum endothelial inflammatory markers including high sensitivity C-reactive protein (hs-CRP), IL-6, TNF-alpha, and fasting lipid profile including ApoA1 and ApoB. 
Glycemic control will be evaluated by measuring fasting blood glucose, insulin, and HbA1c levels and assessing insulin resistance using HOMA-IR
 
 • Adiposity, measured using the Tanita Body Composition Analyzer scale, measured as percentage body fat. • Estimation of Creatinine clearance and Proteinuria estimation. • Vessel health will be assessed by systolic and diastolic blood pressure and Arterial stiffness assessed using vascular flow and wave measurement equipment, SphygmoCor CP system from ATCOR. • The sphygmocor system also allows us to estimate central and aortic blood pressure. • Resting Metabolic Rate (RMR, similar to Resting Energy expenditure measurement) at baseline, midway point (week 6) and post therapy.
--	---

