2 STUDY OBJECTIVES

2.1 Primary Objective

To investigate the effect of Linagliptin on Endothelial progenitor cells (CD34 positive cells) in patients whose HbA1C is between 6.5 to 10% (both inclusive) while being on treatment with a stable dose of insulin, Metformin, or both for the preceding 3 months before enrollment.

Cellular markers: We will use patient's peripheral blood derived CD34+ cells looking at number, function and gene expression changes pre and post Linagliptin over 12 weeks of therapy.

Urinary Function Marker in CKD: We will estimate 24hr urinary protein estimation and creatinine clearance (This is measured via the micro-albumin/Creatinine ratio provided from a random spot urine sample).

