2.2 Secondary Objectives

To investigate the effect of Linagliptin treatment on serum endothelium inflammatory markers including: C-reactive protein (hs-CRP), IL-6, TNF-alpha, and fasting lipid profile including ApoA1 and ApoB (5, 6, 30, 36).

Glycemic control will be evaluated by measuring fasting blood glucose, insulin levels and HbA1c. Fasting blood glucose, insulin and lipid profile will be used to assess insulin resistance (32, 37)

Adiposity will be measured using the Tanita Body Composition Analyzer scale, measured as percentage body fat (33). Serum will be used to estimate levels of SDF1-Alpha, VEGF, and GLP1 levels by ELISA (25, 28, 29, and 30).

We also intend to follow resting Metabolic Rate at baseline, midway, and post DPP4 inhibitor therapy to ascertain if Linagliptin has any effect on RMR (56).

Kidney health will be monitored by creatinine clearance and microalbumin/ creatinine levels, which will be obtained from the spot urine sample.

- a. *Subjects will have the option of opting into a sub-study that is being where 10-20 mL of the excess fresh spot urine that has been collected will be used for exosome analysis. This is optional, and is not required of subjects. For details of urine-exosome study please see the appendix.*

[figure not shown]
The biochemical or bio-inflammatory markers are an important marker of endothelial inflammation and dysfunction along with glycemic markers and markers of arterial stiffness (36-43, 55, 57). Literature suggests that DPP4 inhibitors and GLP1 modifies and modulates hemopoietic stem cells and vaso dilatation (37, 44, 45).

Vessel health will be assessed by degree of arterial stiffness, using arterial tonometry. The central and the aortic pressure is assessed by pulse wave analysis (PWA) and pulse wave velocity (PWV) . Arterial stiffness will be assessed using vascular flow and wave form analysis equipment, SphygmoCor CP system from ATCOR. (56)

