APPENDIX A: OPTIONAL URINE EXOSOME STUDY

A urine sample is already required as a part of [name] protocol. This urine will be used for urine pregnancy tests (if applicable), and labcorp tests for microalbumin/creatinine ratio. There will likely be excess urine.

Subjects will have the option to opt in or out of a research study in which the urine will undergo a urine exosome analysis.

Purpose of this Study: Exosomes are cell-derived vesicles that are present in many and perhaps all biological fluids, including blood, urine, and cultured medium of cell cultures. The reported diameter of **exosomes** is between 30 and 100 nm, which is larger than LDL, but much smaller than for example, red blood cells. Exosomes are either released from the cell when multivesicular bodies fuse with the plasma membrane or they are released directly from the plasma membrane.^[3] Evidence is accumulating that exosomes have specialized functions and play a key role in, for example, coagulation, intercellular signaling, and waste management.^[1] Consequently, there is a growing interest in the clinical applications of exosomes. Exosomes can potentially be used for prognosis, therapy, and biomarkers for health and disease. In this study we are particularly interested

in exosomes released from podocytes as a marker of podocyte function and podocyte inflammation. Podocytes are often considered a modified endothelium and one of its more commonly used parameter is microalbuminuria. In this study we are using urine exosomes as an added parameter of kidney function other than microalbuminuria and GFR calculation.

The procedure for this study is as follows:

From this sample, 10-20 mL of the fresh spot urine (or as much as possible) is placed into a urine cup containing 1 tab of cOmplete Ultra - protease inhibitor cocktail (Roche) for exosome analysis. The specimen can be refrigerated at 4°C for ~ 1 week or frozen at -80°C until assay, or will be processed for exosomes as follows;

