Spot urine for exosomes isolation has been successfully employed in our laboratories from ~15 ml urine using a differential centrifugation method^{2,3}. The supernatant will be subjected to ultracentrifugation, with final centrifugation at 200,000g for 2 hr at 4°C to obtain the urinary exosome pellet. The pellet will be tested for exosomes markers, namely CD63, CD9, CD81, Hsp70, and WT-1, nephrin and podocalyxin, using one of two methods. Preferably mRNA will be extracted and then RT-PCR will be run. Alternative analysis will be done using gel electrophoresis followed by Western blot techniques.

Method 1: Urine exosome mRNA extraction

mRNA extraction from exosomes will be accomplished by using commercial kits (Norgen Biotek Corp., Catalog # 47200). Thereafter, a pre-amplification step will take place, this is a necessary step to measure mRNA in exosomes and will be followed by quantification of specific endothelium and podocyte proteins such as CD9, WT-1, nephrin and podocalyxin by RT-PCR.

Total urinary protein content, albumin and creatinine will be measured via Lapcorp for the same urine samples that have been collected.

Method 2: Gel electrophoresis and Western blot

Exosome pellet will be dissolved in Laemli buffer and proteins will be resolved by gel electrophoresis (4-12% polyacrylamide gel) under denaturing conditions. Subsequently, proteins will be transferred to a PVDF membrane by Western blotting using a dry blotting method (iBlot). The blot will be incubated with blocking solution for 1h, and subsequently exposed to a solution with the first antibody overnight, at 4°C. After washing (5 x 5 min), the membrane will be exposed to a secondary antibody (horseradish peroxidase [HRP]-conjugated) for 1h at room temperature. Finally, the membrane will be incubated with an HRP substrate reagent to reveal the proteins bound to the antibodies tested. Quantitative analysis will be performed by densitometry readings of the positive signals corrected to creatinine concentration of the urine aliquot equivalent to each exosome sample.

End-point: Exploratory but in conjunction with urine albumin/creatinine ratio will help to establish impact of Linagliptin on renal function in diabetes related CKD population.

Guidance document for Adverse Events of Special Interest

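### The primary renal outcome is named 24-hour urinary protein and creatinine clearance, but the only assay stated for all patients is a spot albumin/creatinine ratio, which measures neither

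*Combined protocol and SAP*

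**What the plan says.** The synopsis gives the renal part of the primary objective as "24hr urinary protein estimation and creatinine clearance (obtained via micro-albumin/creatinine ratio from a spot urine sample", and repeats 24-hour protein and creatinine clearance among the primary outcome measures. Section 2.1 has the same pairing: "We will estimate 24hr urinary protein estimation and creatinine clearance", followed by the explanation "This is measured via the micro-albumin/Creatinine ratio provided from a random spot urine sample".

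Section 2.2 returns to the kidney as a secondary matter: "Kidney health will be monitored by creatinine clearance and microalbumin/ creatinine levels, which will be obtained from the spot urine sample". The synopsis likewise lists creatinine clearance and proteinuria a second time, under secondary outcomes. The list of secondary measures in Section 4.5 includes creatinine clearance and a proteinuria estimate from random spot urine, without naming the analyte.

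The Time and Events Schedule in Section 4.5 has a spot urine for every patient at screening and at weeks 0, 6 and 12. It has no 24-hour collection.

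Appendix A says what the required urine is for: pregnancy tests where applicable, and "labcorp tests for microalbumin/creatinine ratio". On the exosome work it says "Subjects will have the option to opt in or out of a research study". Under Method 1 it adds "Total urinary protein content, albumin and creatinine will be measured via Lapcorp for the same urine samples that have been collected". The appendix describes its endpoint as exploratory, to be read together with the albumin/creatinine ratio.

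**The concern.** The name of a primary outcome should identify the variable that will be analysed. Here the name is total protein over 24 hours, and the stated measurement is albumin relative to creatinine in a single voided sample. A report that linagliptin did or did not improve 24-hour urinary protein would describe a quantity that the main study does not state it measures.

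The mismatch also leaves room for choice after the data are seen. The all-patient albumin ratio, an unspecified proteinuria estimate and the appendix total protein could each be presented as the renal result. Renal measures that appear under both primary and secondary headings make that easier.

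**Working it through.** The plan gives no sample size, power or effect figure for the renal outcome; its calculations concern CD34+/KDR+ cells and VEGF. The check is therefore a comparison of the texts, with one piece of illustrative arithmetic.

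**1. What is measured, and in whom**

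| Place | Quantity named | Measurement stated | Patients |
|---|---|---|---|
| Synopsis, primary objective | 24-hour protein, creatinine clearance | Spot microalbumin/creatinine ratio | All 40 |
| Section 2.1 | 24-hour protein, creatinine clearance | Spot microalbumin/creatinine ratio | All 40 |
| Section 2.2 | Creatinine clearance, microalbumin/creatinine | Spot urine | All 40 |
| Section 4.5, secondary measures | Creatinine clearance, proteinuria | Spot urine, analyte not named | All 40 |
| Appendix A, opening | Microalbumin/creatinine ratio | Laboratory test on the required urine | All 40 |
| Appendix A, Method 1 | Total protein, albumin, creatinine | Laboratory test on the same samples | Inside the optional sub-study |

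Every all-patient row that names an analyte names albumin. Appendix A also presents exosomes as an addition to microalbuminuria and calculated GFR, which again describes the main study's renal measures as albumin and a GFR estimate.

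**2. Does the ratio give protein?**
Total protein = albumin + non-albumin protein. The ratio carries only the first term. If albumin is a fraction f of total protein, then total protein = albumin / f, and f is not measured. The documents give no value for f. For an assumed range of 0.20 to 0.70:
- f = 0.70: 1 / 0.70 = 1.4 times the albumin value
- f = 0.20: 1 / 0.20 = 5 times the albumin value

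Unless f is known and stable, neither the level of total protein nor its change can be recovered from the ratio.

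**3. Does the ratio give creatinine clearance?**
A measured clearance is (urine creatinine concentration × urine volume per unit time) / serum creatinine concentration. The ratio is urine albumin / urine creatinine. It has no timed volume and no serum creatinine, so clearance does not follow from it. Section 3.2.1 describes estimating GFR from serum creatinine for CKD staging, but no section states that this supplies the outcome.

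**4. Does taking part in the sub-study change the primary outcome?**
No. The synopsis and Section 2.1 define the measure through the spot ratio, and the schedule gives that sample to everyone. The appendix assay uses the same spot urine, so joining the sub-study would not supply a 24-hour collection either.

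**The case against.** The best defence is that the plan is open about its method. It speaks of an estimation, and both primary statements say in brackets that a spot ratio is the source. A reader of the protocol is not misled about the specimen or about who provides it. That stands for the specimen. It does not settle the analyte: a spot albumin ratio stands in for albumin excretion, and Appendix A itself treats albumin and total protein as different tests.

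A second defence is that the proteinuria estimate in Section 4.5 may be a total protein test for everyone, and that the same-samples wording in Appendix A may cover all required urine. Neither can be ruled out. Against this, the appendix's own account of the required urine lists only pregnancy tests and the albumin ratio, although it does not say that the list is complete. The ambiguity is a reason to reconcile the passages, not evidence that protein is ordered.

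Two stronger readings are tempting, and the documents do not support them.
- A reader might infer that patients who decline the exosome sub-study have no primary renal outcome. They do have it as the plan defines it, because the ratio is collected in everyone. Any loss of precision from opting out would fall on the exploratory assay alone.
- A reader might infer from the synopsis, where poor progenitor cell function "affects the repair and regeneration of the endothelium and renal tubules", that an albumin measure misses a tubular effect the trial sets out to show. Those words are background. The hypothesis sentence that follows concerns cardiovascular risk through progenitor cell survival and function, and no listed outcome is a tubular protein effect.

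**Conclusion.** The point holds as a mismatch between the name and the measurement of a primary outcome. It affects all 40 patients equally and has nothing to do with sub-study participation. No primary data are lost; what is at risk is the claim that can be made from them. As written, the data described can support a statement about the spot albumin/creatinine ratio, but not one about 24-hour urinary protein, nor one about creatinine clearance derived from that ratio.

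The factor of 1.4 to 5 between albumin and total protein rests on the assumed 20% to 70% share. It illustrates that the two are not interchangeable and does not estimate a bias in the treatment comparison. The conclusion also assumes that the unspecified proteinuria estimate in Section 4.5 is not a separate total protein assay. If it is one, the plan needs to say so.

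**What to change.** Choose one of two changes before unblinding.

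1. **Rename.** In the synopsis and Section 2.1, call the primary renal outcome spot urine albumin/creatinine ratio, remove 24-hour urinary protein, and state that total protein in Appendix A is exploratory. This costs wording only.
2. **Measure.** Add total protein with creatinine to the main spot-urine panel for all patients at weeks 0, 6 and 12, and report the protein/creatinine ratio as the spot estimate beside the albumin/creatinine ratio. This is at most 40 × 3 = 120 low-cost assays on urine already collected. The synopsis plans the first visit for September 2015 and this version is dated June 2017, so patients already seen may lack the assay unless urine was kept.

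With either change, stop attributing creatinine clearance to the ratio and state how it is obtained, or remove it. Name the analyte in the Section 4.5 list, say in Appendix A whether total protein is run on all samples or only on those of sub-study participants, and list each renal variable once, as primary or as secondary. The synopsis, Sections 2.1 and 2.2, the Section 4.5 list and Appendix A should then agree.
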